4. MAP
 - A. All MAP values obtained 24 hours after the first dose of study drug regardless of administration route.
 - B. MAP values will be obtained at a minimum at the following time points
 - i. Prior to the first dose of study drug or dose escalation: 2 hours (\pm 5 minutes), 1 hour (\pm 5 minutes), and 15 minutes (\pm 5 minutes)
 - ii. If administration route is IV:
 - a. During and following the first dose of study drug or dose escalation: MAP at start of infusion, every 15 minutes (\pm 5 minutes) during infusion, at end of infusion (inclusive of flush) (\pm 5 minutes), at 15 and 30 minutes (\pm 5 minutes) after end of infusion, hourly (\pm 15 minutes) for 4 hours, and once in the remaining 2 hours prior to the next dose.
 - b. For subsequent IV doses, the lowest valid MAP value should be recorded daily while on study drug.
 - iii. If the administration route is enteral:
 - a. During and following the first dose of study drug or dose escalation: MAP at start of enteral administration, then every 15 minutes (\pm 5 minutes) for 90 minutes (1.5 hours), then every 30 minutes (\pm 5 minutes) for 60 minutes (1 hour), then hourly (\pm 15 minutes) for 4 hours, then once in the remaining 2 hours prior to the next dose.
 - b. For subsequent enteral doses, the lowest valid MAP value should be recorded daily while on study drug.
5. Respiratory assessment, daily (Section 8.2.2.3)
6. Laboratory evaluations, at least once every 2 weeks (Section 8.2).
7. Echocardiograms and cardiac catheterization reports, if performed per local standard of care
8. PK sampling (after Day 7 [Section 8.2.2.1])
9. Adverse events (Section 9.3)

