5.5 Participant Withdrawal or Discontinuation from Study Procedures/Intervention

5.5.1 *Reasons for Participant Withdrawal or Discontinuation from Study Procedures/Intervention*

The participant's parent or guardian may withdraw an infant from participation in the study at any time. Parents or guardians can choose to have infant discontinue study drug and continue to be followed or they can withdraw consent for further participation at any time.

The site investigator may choose to suspend study drug dosing once for up to 48 hours for any reason. If study drug is resumed by the site investigator, the dose and interval of the study drug will be the same as the prior dose. If applicable, subsequent doses will follow the dose escalation or weaning schedule as specified in section 6.1. If study drug is suspended for > 48 hours, the study drug administration will be discontinued and the participant will proceed directly into the safety follow-up period, during which all remaining assessments will be collected. If study drug is suspended for > 48 hours for a documented safety concern, the suspension will not be considered a protocol deviation.

The site investigator will withdraw a participant from receiving further study interventions, including study drug administration, and the participant will enter the 28-day safety-monitoring period if any of the following occur:

- During the course of the study, the participant meets safety-related criteria that would have led to initial exclusion from study participation (i.e., ALT > 150 U/L, AST > 225 U/L, or infant started on vasopressor or inhaled nitric oxide [Section 5.2]).
- Any clinically significant AE (e.g., hypotension) that is deemed by the site investigator to require discontinuation of study drug (see Section 9.5.3 for the definition of hypotension).
- Unmasking of the participant treatment occurs. All unmasking events should be recorded on a protocol deviation form in the EDC system within 24 hours of the unmasking. The decision to unmask will be made in consultation with the medical monitor.

Before discontinuing a participant from the study drug, the site investigator must contact the medical monitor or study PI, except in emergencies. All participants who have study drug suspended will continue to be in the study and complete all remaining study procedures in the safety follow-up period.

5.5.2 Handling of Participant Withdrawals from Study or Participant Discontinuation of Study Intervention

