6 STUDY INTERVENTION

6.1 Study Product Description

In the US, sildenafil, in both IV and for oral suspension, has been approved for use in other populations and for other indications by the FDA¹.

Study dosing and escalation are described in Table 3. Refer to Section 6.1.3 for study drug packaging and labeling.

Table 3 Number of Participants (N) and Dosing Scheme

Cohort ¹	Treatment Group		Sildenafil Dosing ² (mg/kg q 8 hours)		Total (N)
	Placebo (N)	Sildenafil (N)	IV	Enteral	
1	10	30	0.5	1	40
2	10	30	1	2	40
3	10	30	2	4	40

Abbreviations: IV, intravenous; N, number of participants; q, every

1 Participants will be enrolled into cohorts sequentially (i.e., Cohort 1 then Cohort 2 then Cohort 3) based on safety.

2 Route of administration, IV or enteral, is left to investigator discretion.

Dose escalations for each sequential cohort will proceed as summarized in Table 4. DSMB safety review (Section 10) will be required prior to enrolling the next cohort.

Table 4 Dose Escalations for Each Sequential Cohort

	Study Days (Dose Numbers)							
	1-2 (1-6)	3-4 (7-12)	5-6 (13-18)	7-8 (19-24)	9-10 (25-30)	11-12 (31-36)	13-14 (37-42)	15 + (43 +)
Sildenafil Dose (mg/kg)								
Cohort 1								
IV	0.25	0.5	0.5	0.5	0.5	0.5	0.5	0.5
Enteral	0.5	1	1	1	1	1	1	1
Cohort 2								
IV	0.25	0.5	0.75	1	1	1	1	1
Enteral	0.5	1	1.5	2	2	2	2	2
Cohort 3								
IV	0.25	0.5	0.75	1	1.5	1.75	2	2
Enteral	0.5	1	1.5	2	3	3.5	4	4

Abbreviation: IV, intravenous

Dose escalation will occur if the infant is:

1. Receiving exogenous oxygen or respiratory support (nasal cannula or positive pressure from any device); and
2. AST < 225 U/L and ALT < 150 U/L at last check (within 14 days) prior and closest to dose increase.

An infant will meet respiratory criteria for dose escalation only if the infant is receiving exogenous oxygen or respiratory support (nasal cannula or positive pressure from any device) for at least 12 hours before the dose escalation. Infants who do not initially qualify for escalation should be reevaluated daily to ascertain whether they meet these criteria, and escalation must occur within 24 hours of an infant meeting all dose escalation criteria (respiratory and laboratory). If escalation does not occur within this timeframe, then a protocol deviation must be recorded.

Adjusting dose for weight

The actual weight should be reviewed weekly (plus or minus one day, Section 4.2) and the dose of the study drug may be adjusted.

Weaning Period Schedule

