Sildenafil is commonly used at higher doses to treat PH in infants. In clinical practice, it is recommended to wean from these higher doses to prevent rebound effects that may be seen with abrupt discontinuation of sildenafil. Although sildenafil used in this study is for prevention of PH, the target doses in Cohorts 2 and 3 are similar to those used for the treatment of PH.

For Cohorts 2 and 3, weaning of study sildenafil or placebo will begin following the last study dose on Day 28 or if the dose escalates to a dose of ≥ 0.5 mg/kg IV or ≥ 1 mg/kg enteral and the participant is withdrawn from the study. Wean by 25% of last study dose every 2 days until off. Participants should complete weaning after 6 days (Table 5).

Table 5 Weaning Schedule for Study Sildenafil or Placebo in Cohorts 2 and 3

Weaning Days	IV	Enteral
1-2	75% of last study dose	75% of last study dose
3-4	50% of last study dose	50% of last study dose
5-6	25% of last study dose	25% of last study dose
7	Discontinue	Discontinue

Abbreviation: IV, intravenous

If a participant in Cohort 2 or 3, escalates to a dose of ≥ 0.5 mg/kg IV (or ≥ 1 mg/kg enteral) and then is withdrawn from study drug, they will be withdrawn using the weaning schedule outlined above. Deviation from the weaning schedule for documented safety concerns will not result in a protocol deviation.

Weaning is not required for participants in Cohort 1 as the risk of rebound effects is likely minimal for infants receiving low-dose sildenafil.

6.1.1 *Study Placebos*

Intravenous placebo is sterile saline or dextrose 5% and enteral placebo is dextrose 5%.

6.1.2 *Acquisition*

Study drug and placebo will be acquired from the hospital pharmacy. Enteral sildenafil will be supplied to the site pharmacy by Pfizer, Inc. and will be labelled for investigational use. IV sildenafil will be supplied by the site using commercially available products (“off the shelf”).

6.1.3 *Formulation, Packaging, and Labeling*

Intravenous formulation: Only marketed IV formulation for IV administration will be used. This protocol will not specify the brand of product. Each product will be “off the shelf” as provided by the site’s pharmacy. Placebo will be an equal volume of sterile saline or dextrose 5%.

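### The within-infant escalation rule in Section 6.1 ignores blood pressure and has no safety exemption, so a hold at a tolerated dose beyond a short delay is not clearly permitted

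*Combined protocol and SAP*

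**What the plan says.** Section 6.1 provides that a scheduled dose increase will take place if the infant has been on oxygen or respiratory support for at least 12 hours and the latest AST and ALT are under 225 and 150 U/L. For timing, the text reads "Infants who do not initially qualify for escalation should be reevaluated daily to ascertain whether they meet these criteria", and the same sentence goes on to say that "escalation must occur within 24 hours of an infant meeting all dose escalation criteria (respiratory and laboratory"). It adds: "If escalation does not occur within this timeframe, then a protocol deviation must be recorded".

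Section 4.2 requires MAP before every step ("Prior to the first dose of study drug or dose escalation: 2 hours", then 1 hour and 15 minutes) but attaches no decision to the readings.

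Two neighbouring rules do make room for safety. On suspension, 5.5.1 says: "If study drug is suspended for > 48 hours for a documented safety concern, the suspension will not be considered a protocol deviation". On weaning, 6.1 says: "Deviation from the weaning schedule for documented safety concerns will not result in a protocol deviation".

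The short-pause rule in 5.5.1 is: "The site investigator may choose to suspend study drug dosing once for up to 48 hours for any reason". Dosing resumes at the prior dose, and then "If applicable, subsequent doses will follow the dose escalation or weaning schedule as specified in section 6.1".

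**The concern.** Hypotension is the primary outcome (3.2.1), and Section 2.3.1.2 names a fall in blood pressure as a risk of the drug. The rule that increases exposure is nevertheless the one rule of the three that takes no account of a safety concern. Followed literally, it raises the dose of a vasodilator in an infant who has just been treated for low blood pressure, once any short delay is used up.

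The reasonable clinical alternative is to stay at the dose the infant tolerates. On the natural reading that is logged as a deviation, and Section 16.6 then requires the site to develop corrective actions for what was sound care. The other compliant choice is to stop the drug, which loses an infant who might have continued at a lower dose. Section 9.5.2 also counts discontinuations: three in a cohort for the same type of event suspend enrollment for DSMB review.

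There is an information cost too. Section 5.5.2 asks for reasons for discontinuation, but nothing asks why a scheduled step was not taken. In a dose-escalating safety trial, a step withheld for hypotension is tolerability evidence.

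**Working it through.** The plan gives no figure on this point, so the main check is of the text.

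**What each rule allows**

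| Situation | Section | Allowed without a deviation? |
|---|---|---|
| Suspension over 48 h for a documented safety concern | 5.5.1 | Yes, but study drug then ends |
| Departure from weaning for a documented safety concern | 6.1 | Yes |
| One pause of up to 48 h, any reason | 5.5.1 | Yes; prior dose, then back to the schedule |
| Vasopressor started | 5.5.1 | Withdrawal from study drug required |
| Withdrawal at investigator discretion | 9.5.1 | Yes |
| Clinically significant hypotension during a dose | 6.2 | Dose stopped; the clinical team decides on continuing; dose level not mentioned |
| Individual dose modification | 6.3 | Weight only |
| Longer hold at a tolerated dose | 6.1 | No provision |

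The primary outcome also counts hypotension treated with a fluid bolus or systemic steroid (3.2.1). Neither treatment requires withdrawal, so these infants meet the last row.

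**Steps affected (Table 4, IV).** 0.25→0.5 (+100%), →0.75 (+50%), →1 (+33%), →1.5 (+50%), →1.75 (+17%), →2 mg/kg (+14%). Cohorts 1, 2 and 3 have 1, 3 and 6 steps.

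**Compliant delay.**
- Window alone: 24 h / 8 h = 3 doses beyond the scheduled 6.
- Pause: 48 h / 8 h = 6 doses. The total delay is 48 h if the window runs during the pause, or 48 + 24 = 72 h if it starts on resumption. Only one step per infant can use it.

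**Example.** A Cohort 3 infant on 1 mg/kg IV receives a bolus on Day 8. The step to 1.5 mg/kg is due on Day 9. It can be put off to Day 10, or to about Day 11–12 with the pause.

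**Scale, for context only.** Spread each cohort's hypotension events evenly over time and count those before the last step.
- Days before the last step: 2, 6 and 12.
- Outcome window: 28 + 28 = 56 days in Cohort 1; 28 + 6 + 28 = 62 in Cohorts 2 and 3. Shares: 2/56 + 6/62 + 12/62 = 0.326.
- On-drug days including wean: 28, 34 and 34. Shares: 2/28 + 6/34 + 12/34 = 0.601.
- Events before the last step = 30 × rate × sum of shares.

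| Rate | Source | Over outcome window | Over on-drug days |
|---|---|---|---|
| 1/34 | Phase 1 (2.2); different design and doses | 0.29 | 0.53 |
| 0.05 | 12.2, detection scenario | 0.49 | 0.90 |
| 0.3 | 12.2, Table 8 precision scenario | 2.93 | 5.41 |

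These are counts out of 90 sildenafil infants. They include infants who would be withdrawn or who need only a short delay. Clustering of events early in treatment would raise them. The two 12.2 rates are planning scenarios, not expected rates.

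**The case against.** The deviation is partly an inference. The 24-hour clause is the second half of a sentence about infants who did not qualify at first, so the deviation sentence may reach only late qualifiers. That reading is possible. But the opening statement that escalation will occur covers every eligible infant, and Section 16.6 treats any noncompliance as a deviation, so not escalating an on-schedule infant would probably count as well. A text that sites can read two ways needs clarifying in any case.

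Blood pressure does govern dosing elsewhere: hypotension stops the dose, a vasopressor ends treatment, and the clinical team decides on continuing. These protections are real, and they narrow the gap to hypotension treated without a vasopressor, before the last step, in an infant whose clinician wants more than two or three days at the same dose. None of them clearly permits that hold. Section 6.2 speaks of continuing the drug, not of its level.

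The harm may be largely administrative. A hold is logged rather than forbidden, every dose is recorded (4.2), and hypotension is reported within 24 hours (9.2.3), so a missed step could be linked to an event afterwards. This stands in part, and the deviation form may capture a reason; the eCRF and MOP are not available to check.

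The single phase 1 event was attributed to an infusion that ran faster than expected, and this protocol infuses over 60 minutes. That supports a small number.

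Finally, mandatory titration keeps infants at the cohort's target dose, and discretionary holds without a MAP threshold would dilute that. This is a genuine cost, limited by daily re-evaluation and made visible by reporting holds by cohort.

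**Conclusion.** The concern holds and should be fixed. Section 6.1 escalates on respiratory and laboratory criteria alone. It lacks the safety exemption found in two adjacent rules, and it leaves no clearly compliant way to keep an infant at a tolerated dose beyond 24 hours per step, or 48 to 72 hours for one step.

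The conclusion rests on the natural reading of 6.1 together with 16.6, and on the protocol text alone; the MOP and DSMB charter could add guidance but would sit against a mandatory instruction. The investigator keeps the options to pause, stop, or hold and log a deviation. How many infants would need a longer hold cannot be derived and is probably small. The case for change is that the rule bears directly on the primary safety outcome and is cheap to correct.

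**What to change.** 1. Add to Section 6.1: *An infant may be held at the current dose for a documented safety concern, including hypotension (3.2.1) or, in the investigator's judgement, low MAP before the step, with daily re-evaluation. A step delayed or withheld for this reason is not a protocol deviation; the reason is recorded and summarised by cohort.*
2. In Section 8.2.2.1, which ties PK sampling to 7 days at the cohort's target dose, add *or at the dose at which the infant is held*, so that held infants still contribute PK data. The first change stands without this one.

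The cost is two sentences, one phrase and one eCRF field. A few infants may stay below their cohort's target dose; daily re-evaluation limits how long.

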6.1.4 Product Storage and Stability

All study drugs must be stored in a secure area with access limited to the investigator and authorized site staff and under physical conditions that are consistent with product-specific requirements provided in the product labeling.

Detailed information on handling storing and reconstitution is found in the package insert.

6.2 Dosage, Preparation and Administration of Study Product

The investigational pharmacist will be unmasked, and will prepare masked study drug. Detailed information will be included in the MOP. The pharmacy at each site will prepare and distribute the study drug in a masked manner and drug will be administered by the bedside nurse.

Intravenous doses of study drug will be administered as infusion over 60 minutes followed by 30 minutes of flush.

Enteral doses will be administered with feedings. The enteral formulation, if used, will be administered enterally either by mouth, orogastric, nasogastric, gastrostomy tube, or other enteral tubes. For enteral administration in infants receiving bolus feedings, mixing and timing of administration may follow the institutional policy. If there is no specific institutional policy, it is recommended that the study drug be mixed in 10 mL of feedings to be given at the end of the feed. If feeds are administered on pump, timing of administration may follow the institutional policy. If there is no specific institutional policy, it is recommended that study drug be mixed in the last 30 minutes of feeding volume.

If the participant experiences signs or symptoms deemed by the investigator to be clinically significant hypotension or study drug-related SAE, the infusion or feeding will be stopped. Continued study drug administration will be decided by the clinical team.

Refer to the MOP for specific details and recommendations for the use of IV and enteral dilutions for small drug volumes.

6.3 Modification of Study Product Administration for a Participant

As noted in Section 6.1, dosing may be adjusted according to any weight changes determined at baseline, and study Days 7, 14 and 21. DSMB safety review is required prior to enrolling participants to the next cohort (Section 10).

6.4 Accountability Procedures for the Study Product

Site pharmacies will have accountability for the study drug and placebo. Monitoring will be conducted to review compliance.

6.5 Concomitant Medications/Treatments

All drug and/or treatments are permitted while on study. Concomitant medications received within 24 hours prior to start of study drug and those given during the 28-day treatment period will be recorded.

6.5.1 Concomitant Medications of Special Interest

The following medications of special interest will be recorded for the entire study period:

- Furosemide
- Bumetanide
- Chlorothiazide
- Hydrochlorothiazide
- Spironolactone
- Inhaled nitric oxide
- Bosentan
- Epoprostenol sodium
- Milrinone
- Sildenafil

7 STUDY SCHEDULE

7.1 Table 6 Schedule of Study Procedures

	Screen/ Baseline	Treatment	Weaning ¹ Cohort 2 and 3	Follow-up	Final study assessment
Time (Day)	Predose ²	1-28 ³ (± 1 Day)	Weaning Day 1-6	Day 1-28 post last study drug dose	Discharge or Transfer
Informed consent	X				
Randomization ⁴	X				
Demographics ⁵	X				
Physical examination	X			X (weekly)	X
Medical history	X				
Actual Weight	X	X (weekly)		X (weekly)	X
Mean arterial pressure	X	X	Last day of wean	X (weekly)	
Respiratory assessment	X	X ⁶ (daily)	X ⁶ (daily)	X ⁶ (daily)	X
Laboratory evaluations ⁷	X	X (every 2 weeks)	X	X	
Study drug administration		X ⁸	X		
Concomitant medications	X	X	X		
Concomitant medications of special interest ⁹	X	X	X	X	X
Adverse events (including SAEs and ESIs) ¹⁰	X	X	X	X	
Global Rank					X
Echocardiogram	X	X ¹¹	X ¹¹	X	X ¹¹
Cardiac catheterization reports ¹¹	X	X	X	X	X
PK sampling		X (after Day 7)			
Discharge information, including ROP ¹²					X

Abbreviations: AE, adverse event; PK, pharmacokinetics; PMA, postmenstrual age; ROP, retinopathy of prematurity; SAE, serious adverse event

¹ Weaning for Cohort 2 and 3 will begin following Day 28 or following the last day of study drug if participant was withdrawn from study drug prior to Day 28 and the dose was escalated to ≥ 0.5 mg/kg IV or ≥ 1 mg/kg enteral.

² Refers to < 24 hours (except laboratory evaluations) and < 14 days (for echocardiogram) prior to start of study drug that these procedures may be conducted and may be the same calendar date as Day 1; informed consent may be obtained any time prior to the initiation of any study procedures.

³ Collect all safety follow-up and remaining assessments if early withdrawal of study drug occurs during the 28-day treatment period. AE and SAE follow-up is through 28 days post last dose of study drug.

⁴ Randomization will occur on Day -1 (1 day prior to first day of treatment).

⁵ Participant demographics (including birthweight, gestational age at birth) and maternal race/ethnicity will be collected.

⁶ Recorded daily during the treatment, weaning, and follow-up periods.

⁷ If not performed per standard of care, AST and ALT must be performed within 72 hours prior to randomization and at least every 2 weeks during the treatment period. When available, the following labs obtained during the treatment, weaning, and follow up periods will be recorded in the EDC if obtained per standard of care: ALT, AST, platelets, phosphorus, chloride, alkaline phosphatase, and caffeine levels.

⁸ Dosing may be adjusted according to any weight changes determined at baseline, study Days 7, 14, and 21.

⁹ Concomitant medications of special interest will be recorded during the entire study period.

¹⁰ AEs will be collected following informed consent through 28 days post last dose of study drug.

¹¹ If performed per local standard of care

¹² Transfer, discharge, duration of hospitalization or death; record if treatment for ROP was required.

8 STUDY PROCEDURES/EVALUATIONS

8.1 Study Procedures/Evaluations

- A focused medical history of the participant will be extracted from the medical record.
- Concomitant medication information including name, route of administration, and dose will be extracted from the medical record.
- Physical examination including the vital signs (MAP) listed under the study schedule will be extracted from the medical record.
- Echocardiogram images will be uploaded for central review and interpretation at the coordinating center.
- Echocardiogram dates and reports will be collected in the EDC.
- Cardiac catheterization dates and reports will be collected in the EDC.
- Biological specimen collection will be performed per local procedures. See the MOP for further detail about biological specimen handling, storage, and shipping.
- Respiratory assessments will be extracted from the medical record (see Section 8.2.2.3 for more details).
- Discharge information will be extracted from the medical record.
- Protocol-specified MAP values will be obtained per local procedures.
- Blood pressure will be determined using MAP. For each participant, MAPs will be taken as noted in Section 4.2. Mean arterial pressure will be measured using an appropriate size cuff or with an intra-arterial placed catheter that measures continuous blood pressure.

